4.5 Biopsy Procedure

A meeting of study investigators will take place before recruitment to review and ensure standardization of biopsies approaches. Investigators will follow the technique described by Kubo et al. to administer lidocaine during TP-Bx.²⁰ For both transperineal and transrectal approaches, 20 mL of 1% lidocaine will be used, respectively, to standardize local anesthesia. At each site, however, the choice of commercial MRI-targeted biopsy platform will be left to the physicians' discretion.

In both transperineal and transrectal biopsy arms for MRI-targeted biopsy, the number of systematic biopsy cores will be standardized to 12 cores. The technique for TR-Bx is performed as described by Kasivisvanathan et al.²² A total of 12 systematic biopsy cores will be obtained from the peripheral zone of the prostate at the base, mid gland, and apex. Locations of the 12 systematic cores are: Right lateral base, Right lateral midgland, Right lateral apex, Right medial base, Right medial midgland, Right medial apex, Left lateral base, Left lateral midgland, Left lateral apex, Left medial base, Left medial midgland, and Left medial apex. The technique for TP-Bx is performed as described by Urkmez et al.³⁸ Locations of the systematic cores will be obtained as follows: 2 cores each at Right posterior lateral, Right posterior medial, Left posterior lateral, and Left posterior medial, as well as 1 core each at Right anterior lateral, Right anterior medial, Left anterior lateral, and Left anterior medial.

In both transperineal and transrectal biopsy arms, the number of targeted biopsy cores will be standardized to 3 cores per target, with a maximum of three ROIs permitted to be chosen for targeted biopsy. MRI-targeted biopsy registration (i.e., matching of the image of the target on MRI with the real-time image of the prostate during biopsy) may be performed by means of visual registration or software-assisted registration.

De-identified video capture of each site's first 10 TP-Bx and TR-Bx will be distributed for review among investigators to monitor for variation in biopsy technique. Deviations from the technique that may occur during routine clinical care will be recorded for each case, monitored by the WCM DSMC and compared between groups. Research coordinators at each site will randomly select 3 TP-Bx and 3 TR-Bx for video upload every 3 months. Investigators will review and discuss during quarterly video-conferences to ensure consistent procedural fidelity throughout the study.

4.6 Duration of Follow Up

Patients will be followed for approximately 7 days following biopsy to evaluate for adverse events. Subjects experiencing an adverse event beyond 7 days stabilization will be followed until resolution or stabilization.

5. Measurement of Outcomes

5.1 Adverse events

The primary objective of this study is to compare the incidence and severity of infectious complications experienced by patients undergoing TP-Bx versus TR-Bx. Patients will be assessed for complications by way of electronic questionnaire administered 7 ± 2 days post biopsy using a REDCap site hosted at Weill Cornell Medical Center. For patients unable to complete the questionnaire electronically, responses will be obtained via telephone interview. Any patient indicating that they experienced an adverse event will be contacted by the study team to seek further details. Additionally, all relevant medical records will be requested. Adverse events will be classified in accordance with Common Terminology Criteria for Adverse Events (CTCAE) v5.0.

The primary outcomes are infection rates of TP-Bx versus TR-Bx.

The secondary outcomes are patient-reported pain and anxiety, and comparison of noninfectious complications such as bleeding and urinary retention rates, and cancer detection.

Timing for assessment of study variables.			
Assessment	Baseline Pre-Bx	Day of Bx	7-days Post-Bx
Baseline history and physical exam, screening, consent	✓		
Prior Bx (Y/N)	✓		
Prior Bx infection (Y/N)	✓		
PSA	✓		
Indication for Bx	✓		
MpMRI findings	✓		
Randomization: TR-Bx vs. TP-Bx	✓		
Bx infection risk determination for TR-Bx prophylaxis	✓		
Bx completed (Y/N)		✓	
Bx duration (minutes)		✓	
Pain (VAS)		✓	✓
Discomfort (VAS)		✓	✓
TMI Anxiety (Likert 5 levels)		✓	
Decision regret			✓
Adverse events (Y/N) and Bother			
UTI			✓
Sepsis			✓
Urinary retention			✓

Fever	✓
Hematuria	✓
Hematochezia	✓
Hematospermia	✓
UTI diagnosed by HCP	✓
Unplanned HCP contact	✓
Qualitative responses	✓
Bx pathologic outcomes, if cancer:	✓
Gleason grade group(s)	✓
Number of cores positive	✓
Number of cores negative	✓
Maximum cancer core length	✓
Targeted Bx positive (Y/N/NA)	✓
Systematic Bx positive (Y/N)	✓
Location of positive cores	✓

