4.2 Data Collection & Confidentiality

Study data will be prospectively collected from patient medical records and patient surveys. In all participating centers, the site-specific research coordinator will perform baseline data acquisition and medical record abstraction. This data will be entered into standardized clinical report forms housed within a REDCap environment and hosted by WCM. Each patient will be assigned a unique study identifier.

REDCap (Research Electronic Data Capture) is a secure, web-based application designed exclusively to support data capture for research studies. The REDCap platform will be partitioned to permit read/write access only to site-specific records such that individual sites will be able to access records for their own subjects, exclusively. REDCap has a secure email and web-based data collection interface that may be utilized for collecting data. The site-specific research coordinator will determine individual patients' preferred method of survey response

and may collect survey data either through mail, telephone, REDCap, or during an in-person visit.

Only the WCM research coordinator will be able to review de-identified data across sites to conduct data quality checks and share data quality with the study biostatistician.

To ensure accuracy of data entered in the REDCap database from source documents (including surveys and medical record abstract), sites will perform 100% visual review and conduct double data entry for a sample (i.e., 10%) of the data.

Data quality checks will be conducted every 6 months, coinciding with Data Safety and Monitoring reviews.

For protocol deviations fitting immediately reportable criteria, the DSMC's primary concern lies with whether the deviation has the potential to negatively impact subject safety or integrity of study data or whether the deviation places subjects at greater risk of harm (including physical, psychological, economic or social harm). If the DSMC makes determinations that the reported protocol deviation impacts either, it may recommend modifications, suspension or termination of the study.

Interim study findings will be communicated in cases where modifications are recommended. The DSMC will require the PI to submit confirmation to the DSMC that the modification(s) have been made, or to submit a reason why the PI did not agree with the DSMC's recommendation.

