5.3 Biopsy Pathology

The proportion of men diagnosed with clinically significant cancer and clinically insignificant cancer will be compared by biopsy approach. Detection of prostate cancer will be captured from the final pathology report. We will record the prostate cancer grade, number and location of positive biopsies for transrectal (location: left vs. right, medial vs. lateral, apex, mid, and base) and for transperineal (location: posterior medial, posterior lateral, and anterior), as well as the maximum cancer core length (in mm), and total number of negative cores. In order to compare outcomes, prostate cancer grade will be categorized into insignificant (Gleason grade group 1) and clinically significant (grade group ≥ 2).²²

6. Statistical Considerations

We define infection complication as any of the following: (1) fever requiring medical advice or intervention; (2) chills requiring medical advice or intervention; or (3) UTI diagnosed by healthcare professional.⁴¹ We aim to enroll 1,702 (n=682 active surveillance, n=620 prior negative biopsy, n=400 first time biopsy) subjects in this study, with equal randomization between groups. We assume that the infection rate in the transperineal group is 0.5%. Given a one-sided α of 0.10, the power to reject the null hypothesis of no difference in infection rates will be >80% if the event rate in the transrectal group is 2.0%. The event estimate is consistent with published post-transrectal biopsy infection rates range from 1% to 17.5%⁴¹⁻⁴⁹ and the 2017 AUA prostate biopsy guidelines cite an infection risk of 5-7%.³⁷

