APPENDIX

Immediate post biopsy questionnaire

Please ask the patient to fill this out after the biopsy, before they leave the department.

Please check the box corresponding to the number, which describes how you felt immediately after the biopsy procedure:

1. Overall, how much **discomfort** did the biopsy procedure cause you?

2. Overall, how much **pain** did the biopsy procedure cause you?

A horizontal scale with numerical labels from 0 to 10. The scale is divided into 11 equal segments. Below the scale, the labels are: 'No pain' under 0, 'Moderate pain' under 5, and 'Extreme pain' under 10.

3. Overall, how much **fear/anxiety** did the biopsy procedure cause you?

Did you experience the following problems during the 7 days after the biopsy procedure?

1. Fevers

Yes

No

2. Shivering and/or chills, as if you had a flu

Yes

No

3. Blood in the urine ("pee")

Yes

No

4. Blood in the semen (ejaculate or "cum")

Yes

No

5. Blood in the stools ("poop")

Yes

No

6. Acute urinary retention, meaning being unable to pass urine ("pee") which was relieved by putting a catheter into the bladder through the penis

Yes

No

7. Urinary tract infection diagnosed by a healthcare professional (doctor or nurse)

Yes

No

8. Please list any new medications, especially any painkillers or antibiotics, that you have taken since the biopsy. Do not list your regular medications but do list any new medications started related to the biopsy. Only list the medications if you have taken them. An example is given in the first box:

Name of medication	Dosage	Number of doses per day	Number of days
--------------------	--------	-------------------------	----------------

e.g. ciprofloxacin	500mg	2	3

9. Since the biopsy, have you had contacts with hospital services for reasons related to the biopsy, which were unplanned and not part of the routine study visits?

Please answer yes if you have had any unplanned contact with any healthcare staff e.g. doctor, nurse, other. Please also answer yes if you have had any unplanned consultations with healthcare staff over the phone:

Yes

No

10. Since the biopsy, have you had contacts with the community healthcare team for reasons unrelated to the biopsy?

Please answer yes if you have had any contact with any healthcare staff in the community e.g. GP, practice nurse, community nurse, other. Please also answer yes if you have had any consultations with community healthcare staff over the phone:

Yes

No

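### The 7-day infection questionnaire may be answered on Day 5 or 6 with no repeat contact, so infections starting after the answer can be missed

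*Combined protocol and SAP*

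**What the plan says.** Section 5.1 assesses complications by an "electronic questionnaire administered 7 ± 2 days post biopsy", with a telephone interview for men who cannot complete it electronically. Section 5.2 repeats the ±2-day window. The calendar in 4.3 places one post-biopsy adverse-event assessment between Day 5 and Day 9 and notes that it is done by patient questionnaire.

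The form in the Appendix asks: "Did you experience the following problems during the 7 days after the biopsy procedure". Section 4.6 sets the matching follow-up: "Patients will be followed for approximately 7 days following biopsy to evaluate for adverse events". It continues follow-up past that point only for men with an adverse event.

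Further contact depends on a positive answer: "Any patient indicating that they experienced an adverse event will be contacted by the study team to seek further details". The next sentence in 5.1 reads "Additionally, all relevant medical records will be requested". Section 4.2 says more generally: "Study data will be prospectively collected from patient medical records and patient surveys".

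Section 6 begins the endpoint definition with "We define infection complication as any of the following: (1) fever requiring medical advice or intervention". It then adds chills on the same terms and a urinary tract infection diagnosed by a healthcare professional. The definition gives no time window.

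**The concern.** The period the form asks about and the period in which it may be answered do not match. A Day 5 answer leaves Days 6 and 7 unobserved, and a Day 6 answer leaves Day 7 unobserved. No earliest completion day, Day 7 reminder or second contact is written for a man who has answered no.

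An early no is also a complete record. It does not count as missing, so the rule in Section 6 that brings in multiple imputation above 5% missing data would not address it.

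Infections are rare here, with about 21 expected in the whole trial, so a few unrecorded ones change the reported rates visibly. Section 6 plans to report an absolute risk difference with a 95% confidence interval. That figure shrinks in proportion to the events missed, even when both arms lose the same share.

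**Working it through.** **Inputs from Section 6.** "We aim to enroll 1,702" men randomized equally, so n = 1,702 / 2 = 851 per arm. Assumed infection rates are 0.5% transperineal and 2.0% transrectal. One-sided α is 0.10 and stated power is above 80%.

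**Input not in the documents.** q is the share of events missed. It is the share of men answering before Day 7 combined with the share of events that start after their answer, less whatever records recover.

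**Step 1: reproduce the plan's figure.** Expected events are 851 × 0.005 = 4.3 and 851 × 0.020 = 17.0, together 21.3. With pooled variance under the null, p̄ = 0.0125 and

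power = Φ{[Δ − 1.2816 √(2p̄(1−p̄)/n)] / √([p₁(1−p₁) + p₂(1−p₂)]/n)}

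= Φ{[0.0150 − 1.2816 × 0.005386] / 0.005374} = Φ(1.507) = 93.4%.

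A one-sided Fisher test by exact enumeration gives 92.0%. Both agree with the stated figure. Section 6 names logistic regression and Barnard's test; these two calculations are taken as bracketing them closely enough for this purpose.

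**Step 2: illustrate q.** Assume onset uniform over 7 days, answers spread evenly over Days 5 to 9 (one fifth each day), and no recovery from records. Then

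q = 0.2 × 2/7 + 0.2 × 1/7 = 0.6/7 = 8.6%.

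If every man answered on Day 5, still with uniform onset and no recovery, q = 2/7 = 28.6%. Onset concentrated late in the week would raise q; recovery from records would lower it.

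**Step 3: effect of equal loss.** Multiply both rates by (1 − q). The risk difference becomes 1.5 × (1 − q) points and the events missed are 21.3 × q.

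| q | Events missed | Risk difference (points) | Power, normal approx. | Power, Fisher |
|---|---|---|---|---|
| 0 | 0 | 1.50 | 93.4% | 92.0% |
| 8.6% (even spread) | 1.8 | 1.37 | 91.7% | 89.7% |
| 20% | 4.3 | 1.20 | 88.7% | 85.6% |
| 28.6% (all on Day 5) | 6.1 | 1.07 | 85.8% | 81.7% |

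The second row of the power formula uses rates of 0.457% and 1.829%: Φ{[0.01371 − 1.2816 × 0.005153] / 0.005142} = Φ(1.383) = 91.7%. Power falls below 80% only at q of about 0.42 by the normal approximation, or about 0.32 by Fisher.

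**Step 4: relative effect.** The risk ratio stays at 0.25, because (1 − q) cancels. The odds ratio is (0.005/0.995) / (0.020/0.980) = 0.246 with no loss and (0.00457/0.99543) / (0.01829/0.98171) = 0.247 at q = 8.6%.

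**The case against.** The strongest reply is that the questionnaire is not the only source. Sections 4.2 and 5.1 provide for medical records, and every component of the endpoint needs medical advice, intervention or a professional diagnosis, so most such infections should leave a trace. This stands in part: a reader might infer that Day 6 and 7 infections are certainly lost, and the documents do not show that. However, the sentence on records in 5.1 directly follows the one on men who report an event. Neither section says that records are sought for men who report none, or through which day.

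A second reply is that a ±2-day window is ordinary, follow-up is only approximately 7 days, and both arms share the same schedule. This also stands in part. Equal loss leaves the relative effect nearly unchanged, but it does not protect the two rates or the absolute difference.

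A reader might also infer bias between the arms, since allocation is unblinded, coordinators know it (4.1), and only the transrectal arm receives prophylaxis (4.4). Unequal loss would matter more: losing 30% of transrectal events alone would cut power to 73.7%. But the documents give no mechanism or evidence for different response days by arm.

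**Conclusion.** The mismatch is real and is visible in the text. Followed as written, the plan can miss infections that start between an early answer and Day 7, unless records recover them. The likely consequence is infection rates and an absolute difference that are somewhat too low, with a small loss of power. The illustrative size is about 2 of 21 events and a risk difference of about 1.37 rather than 1.5 points. It rests on uniform onset, an even spread of answers, equal loss in both arms and no recovery from records; the documents establish none of these.

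It would be tempting to conclude that the trial becomes underpowered. At the plan's own one-sided 0.10 it does not: power stays above 80% even if every man answers on Day 5 under uniform onset. Figures below 80% at this level of loss appear only with a stricter α, such as one-sided 0.025, which the plan does not use. This is a gap in ascertainment that is worth closing, not a failure of the sample size.

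**What to change.** Choose one of two changes to 4.3, 5.1 and 5.2:

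- open the 7-day form on Day 7 and close it on Day 9; or
- keep Days 5 to 9 and have REDCap automatically re-send items 1, 2 and 7 (fever, chills, diagnosed urinary tract infection) on or after Day 7 to anyone who answered on Day 5 or 6, with the same follow-up on medical advice or intervention.

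In either case, state in Section 6 that primary events are those with onset on Days 0 to 7. State in 5.1 that the medical-record check runs through Day 7 for all men in both arms, whether or not they reported an event. Reporting the day of response by arm would let readers see that timing was similar.

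The first option costs two of the five allowed days and may produce slightly more missing forms. The second costs one short extra message to early responders and avoids that risk. Checking records for every man adds some coordinator work.

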5.2 Pain, Anxiety and Discomfort

A questionnaire will be given to patients immediately after the biopsy and at 7 ± 2 days post-biopsy (Appendix). The questionnaire captures discomfort and pain and fear-anxiety using a numerical rating scale (0-10), with higher scores indicating greater intensity of symptoms. The questionnaire also asks about the presence or absence of adverse events, with reporting of significant adverse events (fever, chills, urinary retention, urinary tract infection, treatment from a doctor) subject to follow-up from study staff.

Infectious complications will be captured as: (1) uncomplicated urinary tract infection (UTI): dysuria, urgency, frequency or hematuria without fever and with or without pyuria (>5 white blood cells per high-powered field or positive leukocyte esterase on urine dipstick) or bacteriuria (≥ 105 colony-forming units/mL); (2) complicated UTI: fever, flank pain, nausea or vomiting with or without pyuria and bacteriuria; (3) urosepsis: criteria for sepsis, severe sepsis, and septic shock³⁹ were combined and categorized as urosepsis.⁴⁰

5.3 Biopsy Pathology

The proportion of men diagnosed with clinically significant cancer and clinically insignificant cancer will be compared by biopsy approach. Detection of prostate cancer will be captured from the final pathology report. We will record the prostate cancer grade, number and location of positive biopsies for transrectal (location: left vs. right, medial vs. lateral, apex, mid, and base) and for transperineal (location: posterior medial, posterior lateral, and anterior), as well as the maximum cancer core length (in mm), and total number of negative cores. In order to compare outcomes, prostate cancer grade will be categorized into insignificant (Gleason grade group 1) and clinically significant (grade group ≥ 2).²²

6. Statistical Considerations

We define infection complication as any of the following: (1) fever requiring medical advice or intervention; (2) chills requiring medical advice or intervention; or (3) UTI diagnosed by healthcare professional.⁴¹ We aim to enroll 1,702 (n=682 active surveillance, n=620 prior negative biopsy, n=400 first time biopsy) subjects in this study, with equal randomization between groups. We assume that the infection rate in the transperineal group is 0.5%. Given a one-sided α of 0.10, the power to reject the null hypothesis of no difference in infection rates will be >80% if the event rate in the transrectal group is 2.0%. The event estimate is consistent with published post-transrectal biopsy infection rates range from 1% to 17.5%⁴¹⁻⁴⁹ and the 2017 AUA prostate biopsy guidelines cite an infection risk of 5-7%.³⁷

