For the REDCap randomization model, randomization of subjects will occur on the data collection form where the randomization field is located. Before a subject is randomized, a 'Randomize' button will appear next to that field. When a user (who has been given appropriate 'Randomize' user privileges) clicks that button, a pop-up box will appear that will allow the user to randomize the subject. After a subject has been randomized, the grouping (i.e. transrectal or transperineal biopsy) will become permanently locked and unmodifiable. The randomization field will always be locked and unmodifiable both before and after randomization has occurred for a subject.

Randomization is unblinded, and research coordinators of respective enrolling sites will inform their patients of the assigned cohort.

Subjects randomized to TR-Bx will receive transrectal biopsy. Subjects randomized to TP-Bx will undergo a second consent discussion with the enrolling investigator, where the risks and benefits of transperineal biopsy will be explained. Subjects can then decide whether to undergo standard transrectal biopsy or transperineal biopsy. Subjects who agree to undergo TP-Bx will sign the second-stage consent form.

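### Two of the three primary-endpoint components rest on a qualifier that the form does not ask about and no rule decides, so it is settled by site staff who know the arm

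*Combined protocol and SAP*

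**What the plan says.** Section 6 (Statistical Considerations) defines an infection complication by three alternatives. The first two are "1) fever requiring medical advice or intervention; (2) chills requiring medical advice or intervention". The third is "UTI diagnosed by healthcare professional".

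In the Appendix, the 7-day questionnaire asks about fevers (item 1) and "Shivering and/or chills, as if you had a flu" (item 2), each as Yes/No with no follow-on question. Item 7 asks directly about a urinary tract infection diagnosed by a professional, so the third component has its own field. Item 8 lists new medications. Item 9 asks about unplanned contact with healthcare staff related to the biopsy.

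Section 5.1 states: "Any patient indicating that they experienced an adverse event will be contacted by the study team to seek further details". It adds that relevant medical records will be requested. Section 4.2 gives record abstraction to the site research coordinator. Section 4.1 states: "Randomization is unblinded, and research coordinators of respective enrolling sites will inform their patients of the assigned cohort".

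On size, Section 6 says "We aim to enroll 1,702 (n=682 active surveillance, n=620 prior negative biopsy, n=400 first time biopsy) subjects in this study", "with equal randomization between groups", with assumed rates of 0.5% (transperineal) and 2.0% (transrectal). Power above 80% is claimed "Given a one-sided α of 0.10".

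**The concern.** The trial cannot be blinded to patients or operators, so its protection against biased counting has to come from an endpoint rule that leaves little to judgement. For fever and chills the judgement lies exactly at the line between a reported symptom and a primary event. The form records the symptom, but whether it required advice or treatment is established afterwards by people who know which biopsy was done. The protocol's background treats the transrectal route as the infection-prone one, so those people may hold an expectation. Few events are planned for, and the hypothesis is tested one-sided at 0.10. A small number of arm-dependent decisions could move the result.

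**Working it through.** **1. What decides whether a fever or chill counts**

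| Source | What it gives | What it lacks |
|---|---|---|
| Items 1 and 2 | Symptom, Yes/No | Any mention of advice or treatment |
| Item 8 | New medications, including antibiotics | The reason for taking them |
| Item 9 | Unplanned biopsy-related contact, Yes/No | The symptom behind it; retention or bleeding would also give a yes |
| Item 10 | Community healthcare contact | It is worded for contact not related to the biopsy |
| Follow-up contact (Section 5.1) | Further details | A rule, a script, masking to arm |
| Medical records (Sections 4.2, 5.1) | Documented care | Masking to arm; advice by telephone may leave no record |

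No section says how these sources combine into components (1) and (2).

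**2. The plan's own figure**

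Inputs from Section 6: n = 1,702 / 2 = 851 per arm; p(TR) = 0.020; p(TP) = 0.005; one-sided alpha 0.10, z = 1.2816.

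- Pooled rate = 0.0125. SE under the null = √(0.0125 × 0.9875 × 2/851) = 0.005386.
- SE under the alternative = √((0.02 × 0.98 + 0.005 × 0.995)/851) = 0.005374.
- Power = Φ((0.015 − 1.2816 × 0.005386)/0.005374) = Φ(1.507) = 93.4%.

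An exact one-sided Fisher calculation gives 92.0%. The stated power above 80% is met and is not in question. Expected events are 851 × 0.020 = 17.0 and 851 × 0.005 = 4.3.

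**3. Counting that differs by arm (illustrative)**

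The documents give no misclassification rate. Assume a true rate of 1.0% in both arms, and that a further 2% of men per arm (851 × 0.02 = 17) report fever or chills without having sought care. A share of these is upgraded to events. The test is a one-sided unconditional pooled-z test of Barnard type, with size held at or below 0.10 and the rejection probability obtained by exact enumeration.

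| Upgraded in TR / TP | Extra TR / TP events | Counted rates TR / TP | False-positive rate |
|---|---|---|---|
| 0% / 0% | 0 / 0 | 1.0% / 1.0% | 8% |
| 10% / 0% | 1.7 / 0 | 1.2% / 1.0% | 16% |
| 25% / 0% | 4.3 / 0 | 1.5% / 1.0% | 32% |
| 10% / 5% | 1.7 / 0.9 | 1.2% / 1.1% | 11% |
| 25% / 12.5% | 4.3 / 2.1 | 1.5% / 1.25% | 17% |

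The pattern does not depend on the base rate or the test. With 4.3 extra TR events (0.5 points), Fisher's test rejects in 26.4% of trials at a 1.25% base rate and 35.5% at 0.5%. An uncorrected pooled z-test gives 33.8% and 47.1%.

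**4. Counting that is equally loose in both arms**

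Start from the planned 2.0% versus 0.5% and add the same number of points to each arm. By the formula in step 2, power falls from 93.4% to 86.0% (+0.5 points), 79.0% (+1.0) or 67.9% (+2.0). False positives do not rise; the contrast is diluted.

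**The case against.** The form is not silent on care. Items 8 and 9 record new medications and unplanned contact, and a yes to fever with a yes to item 9 is already a patient-reported signal given before the follow-up call. Medical records are a second source. The follow-up contact is triggered in the same way in both arms. The Appendix may also not show the whole instrument, since the Section 5.1 table lists bother, decision regret and qualitative responses that do not appear there. All of this stands, and it narrows the point. It does not supply a symptom-linked field, a decision rule or masked classification.

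Four stronger readings are tempting and are not supported:

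- *The study's own call counts as medical advice.* The documents do not say so. Section 5.1 describes the contact as fact-finding, and item 9 leaves out routine study visits. Section 6 does not exclude it either, so its status is undefined. If it were counted equally in both arms, the result would be dilution (step 4), not differential counting.
- *The bias favours the transperineal arm.* The direction is not established. Section 4.4 gives transperineal patients no antibiotic prophylaxis, so staff might take a fever more seriously in that arm.
- *The second consent discussion, held only for the transperineal arm, changes care-seeking.* This is conjecture. It has no stated direction and does not arise at sites using one-stage consent.
- *Two to four men decide the trial.* At those numbers it still fails to reject in 68% to 84% of cases.

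**Conclusion.** The concern holds in a limited form. The fever and chills qualifier has no symptom-linked item and no decision rule, and it is resolved by unblinded site staff with no arm-masked classification described. That much can be read from the text. That judgement would in fact differ by arm is a credible risk only.

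The size, a rise in the false-positive rate from about 8% to about 16–32%, rests on three assumptions outside the documents: a 1.0% true rate in both arms, 2% of men with untreated symptoms, and upgrading in the transrectal arm alone. Upgrading half as often in the other arm reduces it to about 11–17%. The stated power is not in error. This is a cheap improvement worth making, not evidence that the trial's result would be wrong.

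**What to change.** 1. Add to items 1 and 2 a sub-question that the patient answers before any follow-up call: *Did you contact, or were you treated by, a healthcare professional because of this fever/these chills?* (yes/no, date).
2. In Section 6, derive components (1) and (2) by a fixed rule from that answer or from a medical record of advice or treatment for the symptom. Apply the rule centrally, without the arm variable.
3. State that the study team's fact-finding contact is not by itself medical advice, and that treatment or care actually received for the symptom still counts, including after the call. Counting only care that preceded the call would drop a man with a genuine fever who was treated afterwards, and would change the endpoint rather than clarify it.

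The cost is two form items, a short addition to Section 6 and a programmed derivation. The event count may be slightly lower. Patients still know their arm, so self-report remains open-label; the change reduces staff discretion and does not remove reporting bias.
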